### **B. Study Objectives**

**Aim 1:** Test the neurobehavioral adaptions in response to repeated intake of branded SSBs relative to unsweetened, flavored control beverages (USB).

*We hypothesize that daily SSB intake will lead to:*

- a. *increases in parietal/occipital brain response during exposure to the SSB brand;*
- b. *decreased dorsal prefrontal and hippocampal response to the SSB brand;*
- c. *reduced striatal response during receipt of the assigned SSB,*

*relative to baseline and to those who are assigned to consumed the control beverage.*

**Aim 2:** Test whether BMI mediates the neurobehavioral response patterns to the consumed beverages as a function of daily SSB intake relative to baseline and to those who are assigned to consume USB.

*We hypothesize that there will be no significant interaction, such that those individuals with elevated BMI will show no difference than those at a lower BMI in the brain adaptions described in Aim 1.*

**Aim 3:** Test the impact of repeated consumption of SSBs on behavioral responses (reaction time and response inhibition) to the beverage brands measured by the stop sign task (SST).

*We hypothesize that mean reaction time to Go trials will result in a significant interaction of group assignment (sugar vs. control) by pre-/post- daily consumption. Specifically, we hypothesize that the sugar group will show a decreased reaction time to Go trials, representing faster responses relative to the control group and baseline.*

**Aim 4:** Test the impact of repeated consumption of sugar-sweetened beverage on perceptual hedonic and taste ratings.

*We hypothesize that daily beverage intake will lead to:*

- a. *no change in pleasantness and desire ratings as a function of repeated consumption of the assigned beverages.*
- b. *an assignment (sugar vs. control) by time (pre-/post- daily consumption) interaction for desire ratings of the non-assigned beverages. Specifically, we hypothesize that there will be a decrease in desire ratings of the control beverage after having consumed a SSB daily. We expect no change in pleasantness.*

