## E. Study Population

To best capture the local population, we will require that participants have BMI between 18-34 kg/m^2. Following our previous studies, we will exclude young adults who report current: a) contraindications of fMRI (e.g., metal implants), b) serious medical problems (e.g., diabetes) assessed using a standard review form, c) any previous treatment for eating disorders or drug or alcohol abuse/addiction, d) current major psychiatric disorders (e.g., depression, generalized anxiety disorder), e) current dieting, f) regular smoking, and g) dietary practices that do not allow intake of intervention beverages. We will provide samples of the beverages during the consent process to ensure all the participants are willing to adhere to protocols.

Table 1. Assessments	Pre-intervention (2 separate visits)	Intervention (21 days)	Post-intervention (2 separate visits)
fMRI scan	•		•
Fasting blood draw	•		•
Ad lib sugary food intake	•		•
Daily beverage intake		•	
Height/Weight	•		•
Behavioral tasks (incl. SST)	•		•
Explicit perceptual & hedonic ratings	•	X	•
Intake & activity patterns	•		•

X = assigned beverage only

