**Study Session Flow:**

- Internal state ratings (hunger/fullness/thirst/nausea) using VAS
- Begin drinking the 10oz bottle of assigned beverage
- Taste test (of assigned beverage only) & hedonic VAS
- Collection of returned empty bottles
- Distribution of next day's (or weekend's) bottles
- Compensation

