Explicit hedonic, taste and internal state ratings assessed via visual analog scales (VAS). Explicit hedonic scales were used to evaluate characteristics of the beverages, including pleasantness, desire, sweetness, bitterness, intensity, and familiarity insight into alterations the perceptual hedonic value of the beverages. Measures of internal state: hunger, fullness, thirst, and nausea were also collected. For perceptual hedonic assessments, labeled hedonic scales and generalized labeled magnitude scales provide a ratio-like data with the ability to compare individual differences in a more sensitive way than traditional scales. The participant consumed a small amount of the beverage and completed the associated scale (e.g., pleasantness). Additionally, similar internal state scales were assessed via 200mm cross-modal visual analog scales at all assessments. Scales of all beverages (SSB, USB; both flavors) were collected on the pre- and post-intervention behavioral visits. Scales for assigned beverages only were also collected on the pre- and post-intervention scan visits.

Stop signal task (SST). The Stop-Signal Task measures motor response time, accuracy, and response inhibition. The task was performed on an iPad app where participants underwent 6 total runs at the pre-intervention behavioral visit and at the post-intervention behavioral visit. Three of these runs were of their assigned condition, where the logo of their assigned beverage

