For **Aim 4**, perceptual hedonic, taste and internal state ratings (assessed using visual analog scales (VAS)) are analyzed. Data from pre- and post-intervention perceptual ratings are

analyzed using PROC MIXED implemented in SAS (Version 9.4, Cary, NC). Pleasantness and Desire of the assigned beverage (pre-/post-intervention) are each entered into 2x2 repeated measure mixed models, including group-by-time interactions. Control variables of no interest to be included are BMI, assigned flavor, gender, and thirst. Four pairwise comparisons of interest (pre- and post-intervention differences by intervention assignment and within-assignment change over time) are probed. Tukey-adjusted two-tailed  $p$ -values less than 0.05 are considered significant.

**fMRI data preprocessing:** Neuroimaging data were preprocessed using the fMRIPrep pipeline. DICOMS were converted to the Brain Imaging Data Structure (BIDS file structure), then preprocessed using fMRIPrep. Prior to preprocessing, the first four volumes of each functional run were trimmed. fMRIPrep preprocessing included skull stripping using Advanced Normalization Tools (ANTs); tissue segmentation using FSL's Automated Segmentation Tool (FAST); and spatial normalization to Montreal Neurological Institute (MNI) 152-Asymmetrical space using ANTs' registration option. Functional data were co-registered to anatomical data using FSL's FMRIB's Linear Image Registration Tool (FLIRT) with boundary-based registration. Functional data were additionally motion corrected using FSL's MCFLIRT and corrected for fieldmap distortion. In FSL, final preprocessing included spatial smoothing using a 5mm full width half maximum isotropic Gaussian kernel, high-pass filtering, adding temporal derivatives, adjusting for autocorrelation, and adjusting for nuisance regressors, including the 6 motion parameters, 6 anatomical component-based noise correction regressors (aCompCor), and high motion time points (FD>0.5mm). A functional run for a subject was excluded if >30% of total volumes were flagged as high motion points.

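### SAP Aim 4 models only ratings of the assigned beverage, so protocol hypothesis 4b on the non-assigned beverage has no specified test, although the ratings were collected

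*SAP*

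**What the plan says.** Protocol section B gives Aim 4 two hypotheses. Hypothesis 4a expects "no change in pleasantness and desire ratings as a function of repeated consumption of the assigned beverages". Hypothesis 4b expects an assignment-by-time "interaction for desire ratings of the non-assigned beverages", and then makes this specific: "there will be a decrease in desire ratings of the control beverage after having consumed a SSB daily". It adds that pleasantness should not change.

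In SAP section B.1, the Aim 4 text opens by saying that perceptual ratings are analyzed with PROC MIXED and names no beverage. The models it then specifies are these: "Pleasantness and Desire of the assigned beverage (pre-/post-intervention) are each entered into 2x2 repeated measure mixed models". They include group-by-time terms, with BMI, assigned flavor, gender and thirst as covariates. Four pairwise comparisons follow, with Tukey adjustment.

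On data collection, protocol section G says: "Scales of all beverages (SSB, USB; both flavors) were collected on the pre- and post-intervention behavioral visits". It adds: "Scales for assigned beverages only were also collected on the pre- and post-intervention scan visits".

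**The concern.** Hypothesis 4b is about how a participant rates the drink they were not given. The SAP models take each participant's rating of the drink they were given. An SSB participant's desire for the USB, which is the quantity 4b names, is therefore the outcome of no stated model.

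Followed as written, the plan reports on 4a, which predicts no change, and is silent on the one Aim 4 hypothesis that predicts a change. If 4b is analyzed anyway, the analyst must choose the drink, the flavor (both were rated), the visit and the contrast with nothing written down, after the data are in hand.

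**Working it through.** The documents give no design figure for 4b to reproduce. The check is a comparison of texts and a count.

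**1. Is there a 4b model elsewhere in the SAP?** Section A covers sample size and eligibility. Section B.1 covers behavioral data handling, Aim 3 (stop-signal reaction times), Aim 4 and the fMRI analyses. Section B.2 covers questionnaire subscales. Only the Aim 4 text models beverage ratings as outcomes, and only for the assigned beverage. The data-handling text says VAS ratings were summarized descriptively, which is not a test.

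**2. Were the ratings collected?** Protocol section G says so for the behavioral visits. The restriction "X = assigned beverage only" under Table 1 marks the intervention column only. The line "Taste test (of assigned beverage only) & hedonic VAS" belongs to the intervention visits. These two do not contradict section G, which remains the only affirmative source. Scan-visit ratings cover the assigned beverage alone, so a 4b model has to use the behavioral visits.

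**3. Which series are modeled?** Within one flavor there are 2 arms x 2 drinks x 2 scales (desire, pleasantness) = 8 pre/post series.

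| Arm | Drink rated | Status | Series | SAP outcome? |
|---|---|---|---|---|
| SSB | SSB | assigned | 2 | yes |
| SSB | USB | non-assigned | 2 | no |
| USB | USB | assigned | 2 | yes |
| USB | SSB | non-assigned | 2 | no |

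The SAP uses 4 of the 8, and hypothesis 4b rests on the other 4.

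**4. Can the planned interaction stand in for 4b?** Write D(arm, drink) for the mean pre-to-post change in desire.

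- SAP interaction: D(SSB, SSB) - D(USB, USB)
- 4b interaction as worded: D(SSB, USB) - D(USB, SSB)
- 4b specific prediction: D(SSB, USB) < 0
- Same-drink comparison: D(SSB, USB) - D(USB, USB)

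The first expression does not contain D(SSB, USB), so it cannot answer 4b.

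**5. What does each candidate test show?** The interaction as worded compares different drinks between arms. The same-drink comparison removes that difference and is randomized, but the USB is the daily drink in the USB arm. If D(SSB, USB) = 0 and D(USB, USB) = +c, the result is 0 - c = -c. If D(SSB, USB) = -c and D(USB, USB) = 0, it is also -c. The interaction alone cannot tell a fall in the SSB arm from a rise in the USB arm. Each arm's own change must be read with it.

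**6. Precision, for orientation only.** The documents give no SD, correlation or number of rating completers, and the total of 123 in SAP section A is for the primary hypothesis. Assume 123 completers split 62/61 and a pre-post correlation r of 0.5. The standard error of a two-arm difference in change is sqrt(2(1 - 0.5)) x sqrt(1/62 + 1/61) = 0.180 SD, with 80% power at 0.51 SD (two-sided 0.05, unadjusted). Across r of 0.3 to 0.7 and totals of 100 to 160, that figure runs from 0.67 down to 0.35 SD. The finding does not depend on it.

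**The case against.** The best defense is the opening sentence of SAP Aim 4, which says that perceptual ratings are analyzed and does not limit them to one drink. It does not rescue 4b, because it gives no outcome, model or contrast for a non-assigned beverage, and the sentence that does specify models names the assigned one.

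A second objection concerns weight. This is one hypothesis of the last-listed aim, a single sentence would close the gap, and any model added now comes after data collection. That stands, and it keeps the point moderate. It does not excuse silence: both documents carry the same date (January 25, 2023), 4b is a current hypothesis, and nothing says it was dropped.

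A reader might also infer more than the documents support:

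- *That non-assigned ratings enter no model at all.* The Aim 1 and 2 fMRI models adjust for beverage pleasantness without naming the drink. The supportable statement is that these ratings are an outcome in no stated model.
- *That a comparison of USB desire across arms is by itself the test of 4b.* The protocol words the interaction for non-assigned beverages and describes a fall within the SSB arm. As step 5 shows, a change in the USB arm alone could produce the same-drink interaction.
- *That 4b was left out because of its result.* Nothing in the documents shows what was known when the SAP was written.

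**Conclusion.** The gap is real and should be fixed. Hypothesis 4b, covering both desire and pleasantness of the non-assigned beverage, has no specified test, although the protocol says the ratings were taken before and after the intervention. The conclusion rests on the text alone and needs no assumed figure.

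The consequence is limited. The plan as written returns no result for one stated hypothesis and leaves the analysis choices for it open. The planned assigned-beverage estimates are not biased by the omission, and neither are the fMRI tests of Aims 1 and 2.

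**What to change.** Add to SAP Aim 4:

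- Group-by-time mixed models for desire and for pleasantness of the non-assigned beverage, using behavioral-visit ratings, the existing covariates, both the completers and the ITT datasets, and the existing Tukey rule.
- A statement of which flavor rating is used. The stop-signal and fMRI tasks pair each drink with its same-flavor counterpart, but both flavors were rated, so the choice has to be written down.
- The SSB-arm pre-to-post change in USB desire, named as the contrast for the specific 4b prediction.
- A same-drink randomized comparison: USB desire in both arms, group by time. Note that the USB is the daily drink in the USB arm, so the interaction is read together with each arm's own change.
- A label that these analyses were specified after data collection ended (March 2020), and a statement of whether ratings or results had been seen by then.

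Alternatively, declare 4b dropped, give the reason, and draw no conclusion on it.

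The cost is SAP wording and three models in two datasets (3 x 2 = 6 analyses). The ITT analyses also need the added ratings imputed and results pooled over imputations. No new data are needed. The drawback is post hoc status, which must be reported. Dropping 4b costs one sentence but leaves the hypothesis unanswered.

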**4. Post-intervention Scan Visit**

**Occurs:** 2-5 days after the end of the intervention

**Location:** Biomedical Research Imaging Center (BRIC)

**Duration:** 2 hours

**Compensation:** \$80

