**5. Post-intervention Behavioral Visit**

**Occurs:** 1-3 days after the post-intervention scan visit.

**Location:** Neuropsychology of Ingestive Behavior Lab

**Duration:** 1 hours

**Compensation:** \$60

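### Aim 4a concerns ratings under repeated consumption, but the SAP models only a pre/post pair and leaves the nine scheduled intervention-visit ratings without an analysis

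*SAP*

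**What the plan says.** Protocol section B, Aim 4a, predicts "no change in pleasantness and desire ratings as a function of repeated consumption of the assigned beverages". Aim 4b, on the non-assigned drinks, defines time explicitly as before and after the intervention: "an assignment (sugar vs. control) by time (pre-/post- daily consumption) interaction for desire ratings of the non-assigned beverages". Aim 4a carries no such definition.

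Protocol section F.3 lists, for each of nine Monday, Wednesday and Friday visits, "Taste test (of assigned beverage only) & hedonic VAS". Table 1 in section E marks the same ratings in the intervention column ("X = assigned beverage only"), and section H repeats that hedonic ratings are completed at these visits.

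SAP section B.1, Aim 4, states: "Pleasantness and Desire of the assigned beverage (pre-/post-intervention) are each entered into 2x2 repeated measure mixed models". The covariates are BMI, flavour, gender and thirst. Nothing else in the SAP models the intervention-visit ratings. The opening of B.1 mentions descriptive summaries of VAS ratings, and the exploratory section covers questionnaires only.

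On timing, section F.4 puts the post-intervention scan visit "2-5 days after the end of the intervention", and section F.5 puts the behavioural visit "1-3 days after the post-intervention scan visit". Section G says the assigned drink is rated at both kinds of visit, before and after the intervention.

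**The concern.** The hypothesis is about what happens to liking and wanting as the drink is consumed day after day. The modelled post value is taken after daily consumption has ended, and the scheduled ratings that trace the exposure period enter no model. Because 4a predicts a null, this affects how the result can be read. If pre and post agree, two explanations remain open: the ratings never moved, or they moved during the three weeks and had returned by the post visit. The planned analysis cannot distinguish them. The reader also cannot tell how long after the last scheduled bottle the post value was taken, because the SAP does not name the visit that supplies it.

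**Working it through.** **The plan's own figure.** The documents give no power or precision figure for Aim 4. The SAP's detectable effect of 0.25 (alpha 0.05, power 0.80, N = 123) is for the primary hypothesis. Read as Cohen's f for a two-group between-subject comparison, it reproduces: detectable f = 0.2546, and power at f = 0.25 is 0.785. It does not bear on this point.

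**Timing of the post value** (Protocol F.4 and F.5)
- Scan visit: 2 to 5 days after the intervention ends.
- Behavioural visit: (2 + 1) to (5 + 3) = 3 to 8 days after it ends.
- On a strict Monday/Wednesday/Friday calendar, counting the first visit as day 1 of 21, the ninth visit falls on day 19 (Monday start) or day 20 (Wednesday or Friday start). The last intervention rating therefore precedes the post value by (21 - 20) + 2 = 3 days at least and (21 - 19) + 8 = 10 days at most.

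**Ratings scheduled and used**
- Post-baseline ratings of the assigned drink: 9 intervention + 1 scan + 1 behavioural = 11.
- Without a planned model: 9 of 11 if both post visits are used, 10 of 11 if only one is.

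**What fading would do (illustration only).** The documents give no recovery rate. If a change halved every h days after the intervention ended, the share left after t days would be 0.5^(t/h):

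| Assumed half-life | Day 2 | Day 3 | Day 5 | Day 8 |
|---|---|---|---|---|
| 2 days | 50% | 35% | 18% | 6% |
| 4 days | 71% | 59% | 42% | 25% |
| 7 days | 82% | 74% | 61% | 45% |
| 14 days | 91% | 86% | 78% | 67% |

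The scan-visit window is days 2-5 and the behavioural-visit window is days 3-8. The range is too wide to support any particular figure. It shows only that a pre/post null is ambiguous and that the choice of visit matters.

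**Which contrast to take from visits 1-9.** Assume equal variance σ² and equal correlation r between ratings, with equally spaced visits.
- Two-point difference, visit 9 minus visit 1: variance 2(1 - r)σ². A single pre/post difference has the same variance under these assumptions, so the two-point contrast gains no precision.
- Linear trend over nine visits: the squared deviations of 1 to 9 from their mean sum to 60, so the slope has variance (1 - r)σ²/60. The change over 8 steps has variance 8² × (1 - r)σ²/60 = (64/60)(1 - r)σ² = 1.067(1 - r)σ².
- SE ratio: sqrt(1.067/2) = 0.730, so the trend estimate of the same change has an SE about 27% smaller. The factor (1 - r) cancels, so this holds at any r.

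**The case against.** The strongest defence is that pre/post is a legitimate reading of 4a. Aims 3 and 4b use it, every confirmatory analysis in the SAP is built on it, and the protocol's rationale names persistence of adaptations as an interest. It also measures the ratings in the same period as the brain and reaction-time outcomes. That stands: the model is valid, and the gap is that it answers only part of the hypothesis.

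A second defence concerns conditions. Behavioural and scan sessions follow a 4-6 hour fast (Protocol H), whereas at intervention visits the participant starts the bottle before rating (F.3). In one arm that bottle holds 27 g of sugar (section G), so acute effects could differ by arm. This is a good reason not to mix the two sets of ratings. It is largely met by comparing visits 1-9 only with each other, since each is rated after starting the bottle. One limit remains: visit 1 already involves the drink, so this comparison has no pre-exposure baseline taken under the same conditions.

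Third, section G's past-tense account lists hedonic ratings only at the behavioural and scan visits. That the intervention-visit ratings exist is inferred from the schedule, so the added model depends on their having been collected.

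A reader might go further and infer that the post visit is timed to favour the predicted null. The documents do not support this: no passage says that liking falls with repetition or recovers within days. Nor is the interval free of the drink. Study beverages are delivered during the post-intervention scan (section G) and the scan-visit rating follows the scan, so the 2-8 days count from the end of the intervention, not from the last taste.

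**Conclusion.** The point holds as a gap in what Aim 4a can conclude, not as an error in the pre/post model. The SAP tests whether a change in pleasantness or desire remains 2-5 or 3-8 days after the intervention, at a visit it does not name. It plans no model for the nine ratings scheduled during consumption, so a null cannot be read as no change while the drink was being consumed.

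The wording of 4a, the visit windows and the count of 9 (or 10) unmodelled ratings out of 11 come straight from the documents. The half-life table rests on assumed values and measures no bias. The 27% figure rests on equal variances, equal correlation, equal spacing and a linear course. It compares the trend with the visit 1 to visit 9 difference and is not a claim about power for Aim 4. This is a worthwhile, inexpensive improvement to a single aim; it leaves the pre/post analysis intact.

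**What to change.** In SAP B.1, Aim 4:

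1. Keep the 2x2 pre/post model. Name the visit (scan or behavioural) that supplies both the pre and the post rating, and label the estimate as change remaining after the intervention, with the corresponding window.
2. Add a mixed model of assigned-beverage pleasantness and of desire over intervention visits 1-9, with arm, visit (or day), arm-by-visit, the pre-intervention rating and the covariates already listed. Thirst is scheduled at each of these visits.
3. Take the trend across all nine visits and its arm difference as the estimate, with confidence intervals, rather than visit 9 minus visit 1. Plot the visit means so that a non-linear course is visible.
4. Compare visits 1-9 only with each other.
5. Date the addition and label it as a later supplementary analysis, since data collection ended in March 2020 and the SAP is dated January 2023.

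If the ratings were not collected, or the sponsor prefers not to model them, say so and limit the 4a conclusion to change remaining after the intervention. The cost is SAP wording and one more PROC MIXED model for each of two ratings, with no new data collection. The downside is one more reported test per rating.

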### C. Study Design

We propose to use a randomized control trial design and recruit 230 18-28 year old men and women over a 42-month period to address the proposed aims. Participants will be randomly assigned to an experimental condition (sugar-sweetened beverage [SSB] or unsweetened, flavored control [USB]) and then to one of two flavors within their experimental condition. This results in 4 cells: two flavors high-sugar beverages (n=115; 58/57 for each flavor of SSB) and the same two flavors of unsweetened control beverages (n=115; 58/57 for each flavor of control). The two-tiered randomization process allows for a fully powered test of the effects of SSB consumption (n=115) versus unsweetened control (n=115; Aim 1) and individual difference factors (Aims 2-4). Participants will complete the pre-intervention assessments (see **Table 1 & Study Procedures**), then begin the intervention which will include the daily consumption of their flavored beverage for 21 days. Following the intervention, participants will come back in the lab to complete the post-intervention assessments (see **Study Procedures**).

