**G. Study Evaluations and Measurements**

Demographics and Anthropometrics. Self-ported gender, race, and ethnicity were recorded. Height was measured to the nearest mm using a stadiometer. Weight was assessed to the nearest 0.1 kg using digital scales, with participants wearing light clothing without shoes at each assessment. BMI ( $\text{kg}/\text{m}^2$ ) was then calculated.

Intervention beverages & logos. To optimally test the hypothesized sugar-contingent neuroadaptations, the active SSB condition contained 111 kcals and 27g of sugar/10 fl oz (equivalent to the caloric and sugar density of soft drinks), and the unsweetened control beverages used in the study were similarly flavored to SSBs. In a preliminary study, we performed an evaluation of 6 differently mixed fruit flavors of beverages presented in the SSB and unsweetened versions to ensure that the selected beverages are equal in palatability and novelty across flavors. For the pilot, young adults meeting the inclusion criteria proposed here ( $n=27$ ;  $\bar{x}$  BMI =  $23.3 \pm 3.5$ ) rated the mixed fruit strawberry lemonade and mixed fruit cherry orange flavors as equally palatable across flavors, and equally willing to consume daily for 3 weeks in both the SSB and unsweetened versions ( $p's=0.77-0.99$ ). These ratings were not significant impacted by gender or BMI ( $p's=0.46-0.99$ ). Beverages did not include high fructose corn syrup or artificial sweeteners, or preservatives; they are caffeine- and texture-free and generally novel in flavor. Beverages were presented in 10 fl oz bottles (295 mL). To mimic the branding of the beverages, logos were placed on the beverages that correspond with flavors. Logos were selected to be novel, of similar visual complexity, in black and white, and convey no information beyond a unique symbol, and yet be easily distinguishable from one another.

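### The only Aim 4 models compare change in rating of two different drinks, so an arm difference cannot be attributed to repeated SSB intake, and hypothesis 4b has no planned analysis.

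*SAP*

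**What the plan says.** Protocol section B states the purpose of Aim 4: "Test the impact of repeated consumption of sugar-sweetened beverage on perceptual hedonic and taste ratings". It then gives two hypotheses. Hypothesis 4a concerns the assigned drink and predicts "no change in pleasantness and desire ratings as a function of repeated consumption of the assigned beverages". Hypothesis 4b concerns the non-assigned drinks. It predicts an assignment-by-time interaction for desire, specifically that desire for the control drink falls after daily SSB, with pleasantness unchanged.

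SAP section B.1 gives the only Aim 4 models: "Pleasantness and Desire of the assigned beverage (pre-/post-intervention) are each entered into 2x2 repeated measure mixed models, including group-by-time interactions". On covariates it says "Control variables of no interest to be included are BMI, assigned flavor, gender, and thirst". On contrasts it says "Four pairwise comparisons of interest (pre- and post-intervention differences by intervention assignment and within-assignment change over time) are probed", with Tukey-adjusted two-sided p-values.

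The two assigned drinks differ by design. Protocol section G says that "the active SSB condition contained 111 kcals and 27g of sugar/10 fl oz", while the control is unsweetened. The same section describes the available ratings: "Scales of all beverages (SSB, USB; both flavors) were collected on the pre- and post-intervention behavioral visits". Ratings at the scan visits cover the assigned drink only.

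**The concern.** Because the outcome is the rating of whatever drink the participant was given, the drink rated coincides exactly with arm. None of the listed covariates separates them: both flavors occur in both arms, and BMI, gender and thirst do not identify the drink. Two of the four pairwise contrasts, the between-arm ones before and after the intervention, set a rating of a sweetened drink against a rating of an unsweetened one.

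Two things are at stake. First, ratings of the two drinks could move differently between visits for reasons unrelated to daily intake, such as lost novelty or a scale ceiling. The interaction would then carry that difference, and a reader guided by the stated purpose of Aim 4 could take it for an effect of repeated SSB consumption. A drift difference could also offset a real effect. Second, hypothesis 4b, the only Aim 4 hypothesis that predicts an interaction, is about drinks that the planned models leave out.

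**Working it through.** **Structure.** Write the mean pre-to-post change in rating as S1 and U1 for the SSB and USB rated by the SSB arm, and S0 and U0 for the same drinks rated by the control arm. All four can be estimated from the behavioral-visit ratings.

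- Planned interaction: S1 − U0 = (S1 − S0) + (S0 − U0).
- The first bracket is the effect of assignment on the rating of one drink. The second is a difference between two drinks within one arm, which randomization does not set to zero.
- If assignment has no effect on either drink, S1 = S0 = S and U1 = U0 = U, and the planned interaction equals S − U, the difference in drift.
- Same-drink contrasts: S1 − S0 for the SSB and U1 − U0 for the USB. Both are zero when assignment has no effect, whatever S and U are.
- A model of each arm's own non-assigned drink would estimate U1 − S0, which again mixes two drinks. The specific prediction in 4b, a fall in desire for the control drink after daily SSB, is addressed by U1 − U0.

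**Comparison inside the SAP.** The fMRI group model holds the stimulus fixed: its contrasts are SSB against water and SSB logo against water logo in both arms. Aim 4 does not.

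**The plan's own figure.** SAP section A gives a detectable effect of 0.25 at alpha 0.05, power 0.80 and a total of 123, for the primary hypothesis and without naming the metric. A one-degree-of-freedom F test with two groups and N = 123 gives f = 0.2546 (power 78.5% at f = 0.25), so the figure reproduces on that reading. It says nothing about Aim 4; only the sample size is used here.

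**Illustration of size.** Inputs: 61 per arm (123 / 2, rounded down) or 80 per arm (160 / 2), two-sided 5%, and an assumed drift difference d in units of the SD of change. With two time points the interaction is treated as a two-sample comparison of change scores, covariates omitted. The chance of significance with no intake effect is

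P(|Z + d × √(n/2)| > 1.96).

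For n = 61, √30.5 = 5.52; for n = 80, √40 = 6.32.

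| d (SD of change) | shift, n = 61 | significant | shift, n = 80 | significant |
|---|---|---|---|---|
| 0.1 | 0.55 | 9% | 0.63 | 10% |
| 0.2 | 1.10 | 20% | 1.26 | 24% |
| 0.3 | 1.66 | 38% | 1.90 | 48% |

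In units of the rating SD the answer depends on the pre-post correlation r, because SD of change = rating SD × √(2(1 − r)). The documents do not give r. With arms of 61 and 62 (noncentral t):

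| drift difference (rating SD) | r = 0.3 | r = 0.5 | r = 0.7 |
|---|---|---|---|
| 0.2 | 15% | 20% | 30% |
| 0.3 | 29% | 38% | 57% |
| 0.5 | 64% | 79% | 94% |

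A simulation with 10,000 replicates per scenario, no intake effect and drift differences from 0 to 0.5 rating SD gave rejection of 4.5% to 5.4% for the two same-drink contrasts in every scenario, with mean bias within 0.004 SD.

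**The case against.** The strongest reply is that the SAP tests what hypothesis 4a says. That hypothesis is about the assigned drinks, does not name sugar and predicts no interaction. The within-assignment changes it needs are among the planned contrasts, and the SAP nowhere says that the interaction will be read as a sugar effect. This stands, and it is why the assigned-drink changes should be kept. It leaves open the stated purpose of Aim 4, and it leaves 4b without a model.

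A reader might infer that randomization fails here, or that the planned test has an inflated error rate. The documents do not support that. The interaction validly compares change in rating of one's own drink between assignments. The percentages above are wrong conclusions only if the result is read as an effect of intake, and only under an assumed drift. Against 4a's prediction of no change, differential drift would more often contradict the hypothesis than support it; a falsely supportive null needs offsetting effects, for which the documents give no evidence.

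Regression to the mean is another tempting mechanism. It shifts a group mean only after selection on the measured value, and no selection on baseline ratings is described.

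The pilot in Protocol section G (27 people) reports equal palatability across flavors and equal willingness to drink both versions daily. It reports nothing on change over repeated rating, so it neither shows nor rules out a drift difference.

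Finally, the same-drink comparison has no unexposed arm: the other arm drank the other version daily, and 4b itself expects one drink to affect desire for the other. That limits how the new contrast may be described. It does not remove its advantage of comparing one drink across randomized arms.

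**Conclusion.** The point holds as one of interpretation and of a missing analysis. Following the SAP as written, an assigned-drink interaction cannot be attributed to repeated SSB intake rather than to the drink rated, the two between-arm contrasts compare different drinks, and hypothesis 4b is not tested. These conclusions follow from the documents alone.

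The size does not. The documents give no drift, SD or pre-post correlation for the ratings, so the 9%, 20% and 38% at 61 per arm illustrate an assumption and do not estimate this trial's error rate. It would go too far to say that the planned model is invalid, that the drinks are known to drift differently, or that the same-drink models isolate exposure from non-exposure. The fMRI aims are not affected.

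**What to change.** - For pleasantness and for desire, add an arm-by-time model of the SSB of the assigned flavor in all participants and, separately, of the USB of the assigned flavor. Use the behavioral-visit ratings, the only visits at which both drinks were rated.
- Base any between-arm conclusion for Aim 4 on these models, with 4b's prediction read from the USB model for desire.
- Keep the within-arm changes in the assigned drink for 4a. State that the assigned-drink interaction and its between-arm contrasts are not interpreted as an effect of sugar intake.
- Describe each same-drink contrast as the effect of assignment (daily SSB versus daily USB) on the rating of that drink, not as exposed versus unexposed.

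The cost is SAP wording and four further PROC MIXED models (two ratings by two drinks) on each analysis dataset, from data already collected. The downside is more tests, which the multiplicity adjustment should cover. Data collection ended in March 2020 and the SAP is dated January 2023, so the new models should be labelled as added after data collection ended.
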